#### 2.3.4 Participant Confidentiality

All study investigators participating in the current project must ensure that the confidentiality of personal identity and all personal medical information of study participants will be maintained at all times. Additionally, the clinical sites are to follow privacy obligations to study participants under the Health Insurance Portability and Accountability Act (HIPAA). Because the DCU uses a web-based system, source documents will remain at site. The study database and any study documents submitted to the DCU will only identify study subjects by unique study identification codes. All data will be stored in a manner that is HIPAA compliant, without the ability to track the information back to a specific subject except through a password protected system (all collected information about a subject will be stored by a unique identification code). All DCU personnel have received GCP and Human Subject Protection training. All participants will be emailed invitations for telehealth appointments and given instructions in advance to join the telehealth session. Any video recordings made during the assessments will be saved to the researcher's local computer and then transferred to a HIPAAcompliant Box account. The central technology support specialist will have access to participant PHI across sites in order to monitor for video quality, manage Box storage, and call into participant sessions for technology assistance.

#### 2.3.5 Known Potential Benefits

There is no real benefit to participation; however, the information gathered as a result of this study may help others with aphasia in the future. It is possible that the participant may benefit from SET treatment, but not guaranteed.

# 3.0 Objectives and Endpoints

Objectives	Endpoint	Justification			
Primary					
To estimate the dose of SET for individuals with non-fluent aphasia that has the highest effect size on VPM.	Verbs per minute (VPM) at 3 months post-treatment/control period.	*See justification below			
Secondary					
To estimate the dose of SET for individuals with non-fluent aphasia that has the highest effect size on SAQOL-39g.	SAQOL-39g at 3 months post- treatment/control period	To assess if improvements in fluency from SET are related to gains in quality of life.			
Safety and Tolerability	Safety and Tolerability				
To assess the tolerability and safety of SET	Number of treatment sessions completed	Adequate tolerability would be completion of at least 80% of the treatment sessions.			

Exploratory	Adverse Events possibly/probably/definitely related to study treatment and Serious Adverse Events	Although this study intervention is low-risk, there is the potential for risk in any clinical trial.
To estimate the dose of SET for individuals with non-fluent aphasia that has the highest effect size on the WAB-R, CETI, and ASRS 3.0.	Scores at 3 months post-treatment/control period.	To assess if improvements in fluency from SET are related to gains in other speech and/or quality of life measures.
To estimate the effect of SET on VPM, WAB-R, SAQOL-39g at early and late time points.	1-week post and 6 months post	The primary time point of interest is the 3 months post, but the 1 week and 6 month post assessments will be explored to assess whether benefits are sustained over time

\*The primary endpoint for this trial is VPM at three months post-conclusion of SET or control. VPM is a measurable representation of spontaneous speech production. This primary endpoint was chosen for the following reasons:

- 1) Spontaneous speech is an important "real-life" aspect of language. It has a direct effect on conversation and social aspects of language, and directly informs on practical and meaningful elements of communication.
- 2) The use of verbs during spontaneous speech provides a reliable measure of language abilities and effectiveness of communication.
- 3) It is not surprising that many individuals with aphasia can achieve improved fluency during the SET session. However, for SET to have a clinical impact, it should lead to sustained benefits that remain after the therapy. Benefits that can last at least 3 months after therapy are highly important.
- 4) Our preliminary data support that improvement in VPM is a feasible and achievable outcome.

# 4.0 Study Design

# 4.1 Overall Design

Approach: We propose a prospective, controlled, randomized, assessor-blinded, phase II clinical trial (n=80) entitled Speech entrainment for Aphasia Recovery (SpARc). The goals of the trial are to evaluate SET in comparison with no SET (control), and to determine SET's best dose (duration of treatment in weeks). SET and assessments will be delivered via telehealth. We will enroll 80 participants and randomly assign them 1:1:1:1 to one of the 4 groups (A, B, C, D):

- A SET for 3 weeks (15 days, 1 hour daily, 5 x week)
- B SET for 4.5 weeks (22 days, 1 hour daily, 5 x week)
- C SET for 6 weeks (30 days, 1 hour daily, 5 x week)
- D No SET for 6 weeks (control condition)

#### 4.1.1 Timing of Behavioral Assessments

The timing of behavioral assessments after the SET doses, or the control condition (no SET) will exactly mirror each other, so data can be directly compared, and also to permit blinding of the behavioral assessors. The participants will have behavioral assessments at baseline, 1-week post, 3-months post, and 6-months post.

The research staff and the participants will obviously not be blinded to the groups, but the persons doing the scoring of the behavioral outcome measures will be. A scorer will be centrally located at UofSC and will not have contact with the research staff (who will perform the assessments and treatments) and the participants. Another scorer will be located at UoU and will perform scoring of the ASRS 3.0 only. The UoU scorer will not have contact with participants and will also be blinded to treatment arms and assessment time points. All scoring will be performed on videorecorded behavioral assessments stored on Box. By having the same number of follow-up visits, the scorer will not be able to discern the group in which the participant was included. We used this setup successfully in a recently completed randomized controlled trial.

#### 4.1.2 Neuroimaging

We will obtain a release of medical records from all participants and we will review the peri-stroke clinical neuroimaging to confirm that the aphasia was caused by a left hemisphere stroke. We will review brain MRI and/or head CT imaging depending on what modality was used during the stroke clinical care. We will use this information to exclude individuals with previous stroke outside the left hemisphere, and we will only include individuals whose aphasia was associated with a stroke diagnosed with neuroimaging.

For neuroimaging fidelity, the PI will oversee review of participant peri-stroke clinical neuroimaging every six months by trained research staff to ensure that MRI/CT images: (1) are uploaded to the site-specific neuroimaging folder in Box, (2) are converted to Nifti files, (3) are anonymized, (4) are T1-weighted (if MRI scans), and (5) show a left hemisphere stroke (without evidence of right hemisphere stroke).

The participants will be offered to take part in an optional research MRI at follow-up visit 2 or 3. The purpose of the research MRI is to study the brain anatomy in more detail, including the necrotic and gliotic cavity related to the previous stroke.

# 4.2 Scientific Rationale for Study Design

#### 4.2.1 SET vs Control

For SET to be clinically useful, it has to be effective in comparison with a control, no SET condition. The goal of this study is to compare SET with a control condition, in which the individual with aphasia receives baseline and follow-up assessments at the same time-points as group C, however, does not receive therapy for 6 weeks.

Since most individuals with aphasia do not receive continuous speech therapy in the chronic post-stroke stages, it is anticipated most of the control group will not receive treatment

as part of their current standard of care for chronic aphasia. The lack of continuous speech therapy in the chronic stages is, of course, different than in the acute and subacute stages, when continuous speech therapy is often employed. This trial will only assess individuals in the chronic stages. The control condition will provide an important benchmark against variability in speech production across time.

#### 4.3 Justification for Dose

#### 4.3.1 Treatment Groups

In a pilot study, we performed a subsequent and independent assessment of SET to directly mirror the approach proposed in this trial, with a similar endpoint, but uncontrolled and with a single group. Using assessors who were blinded to time of speech assessment (using videorecorded sessions), we examined 15 individuals with chronic non-fluent aphasia who were tested before and after 3 weeks of daily SET sessions. Similar to our published study described above, all participants were able to produce more fluent speech during SET therapy sessions. More importantly, there were considerable gains in spontaneous speech production that were sustained 3 months after SET.

These data, shown in Figure 2, are the main preliminary evidence supporting this study. We observed an increase from an average ( $\pm$  SD) of 5.0 ( $\pm$  3.9) VPM prior to therapy to 6.1 ( $\pm$  4.8) VPM at 3 months after the conclusion of SET. The average relative improvement was 22% (average post-pre difference of 1.11  $\pm$ SD = 1.98), with a standardized effect size (mean difference/SD of difference) of 0.56. This difference was statistically significant (paired t = 2.17, p = 0.047).

#### 4.3.2 Control Group

The control group will be assessed before and after a six week no-SET condition. During the six weeks there will be weekly contact via phone for assessing AEs and concomitant aphasia therapy. This study will include individuals with chronic aphasia. In the chronic stage, large-scale spontaneous language recovery is not typically observed. External treatment for chronic aphasia is not prohibited in this trial. As discussed, there currently is not a standard of care for chronic aphasia. It is anticipated most participants will receive no treatment, some may participate in aphasia community groups, and a very few may receive individualized therapy. Therefore, the expected change in language functioning during the no-SET condition is expected to be very minimal, if any. Concomitant aphasia therapy will be captured (see Table 5).

The behavioral assessments in the control group will occur at the end of the 6-week no SET period. We will not perform behavioral assessments throughout the no-SET period. For example, in the SET for 3 weeks group, the first post-treatment behavioral assessment will be performed at 1 week after treatment conclusion (4 weeks after initiation of the SET). In the control group, there will not be a behavioral assessment in the middle of the no SET period at 4 weeks (or at other times corresponding to the other groups) because multiple repeated assessments may lead to a training effect. They would also interfere with the blinded assessments. Since we do not anticipate any meaningful improvement in the control group, the treatment assessments at 1 week, 3 months, and 6 months after the no-SET condition will be considered equivalent to the post-SET assessments at the corresponding post SET times for

each SET dose. Using the longest possible control duration of 6 weeks ensures adequate sensitivity to any unanticipated improvement during that period. Having multiple control durations to match the SET durations is, therefore, unnecessary and would lead to a prohibitively and impractical sample sizes.

#### 4.4 End of Study Definition

The randomization target for this study is 80 participants. This trial will be implemented in three aphasia clinical research laboratories across the United States: 1- MUSC, 2- UofSC, and 3- UoU. Each site will enroll approximately 25-30 subjects over 4 years.

# 5.0 Study Population

We will only include participants with chronic aphasia (>6 months post-stroke) as a result of an ischemic or hemorrhagic left hemisphere stroke. Clinical imaging (CT/MRI) will be used to verify the presence of a left hemisphere stroke and to exclude those with bilateral, brain stem or cerebellar strokes, or other structural neurological conditions (such as brain tumors or arteriovenous malformations). We will not exclude subjects with previous other left hemisphere strokes, but we will exclude subjects with clinical and radiological evidence of right hemisphere or brain stem or cerebellar strokes with persistent deficits. Subjects will not be excluded if they have received previous aphasia rehabilitation, either in the clinical or academic setting.

#### 5.1 Inclusion Criteria

- Aphasia as a result of a left hemisphere ischemic or hemorrhagic stroke (WAB-R Aphasia Quotient <93.8).

- Presence of left hemisphere stroke in clinical imaging (CT/MRI) and NIHSS
- Participants must have spoken English as their primary language.
- 21-81 years old
- Pre-stroke modified Rankin Scale (mRS)= 2 or less
- Post-stroke mRS= 4 or less.
- At least 6 months post-stroke.
- Non-fluent aphasia (WAB-R Comprehension score >4 and WAB-R Fluency score <6).

- Technological compatibility (to be determined by clinical judgment of SLP)

#### 5.2 Exclusion Criteria

- History of chronic neurological or psychiatric diseases (excluding migraines, depression, or post-stroke epilepsy).
- Self-reported history of learning disability.
- Severe dysarthria (determined via SLP clinical judgment from spontaneous speech tasks on the ASRS 3.0).
- Global aphasia.

- History of right-hemisphere strokes or brain stem/cerebellar strokes with persistent deficits (as evidenced by MRI/CT and NIHSS).
- Uncorrectable hearing as determined by the SLP's clinical judgment.
- Uncorrectable vision.

#### 5.3 Screen Failures

Once a participant has consented, they will be screened for eligibility. This includes reviewing the criteria noted in sections 5.1 and 5.2. The team will review imaging (CT/MRI) obtained from the participant's medical records to verify presence of left hemisphere stroke and absence of strokes involving the right hemisphere, cerebellum, and brainstem that have persistent deficits. The NIHSS will be administered by a trained clinician (e.g., SLP, neurologist) to assess for any persistent neurological deficits. The NIHSS will be used for research purposes only. The WAB-R will also be given to determine if eligible based on the Aphasia Quotient and aphasia classification as non-fluent. If the consenting participant fails either of these tests, it will be considered a screen failure and the participant will not be allowed to continue with the remainder of the trial.

All screen failures will be documented in WebDCU, and a hard copy of the Screen Failure form will be stored in a Screen Failure folder, per IRB regulations. Re-screening of participants is not applicable.

# 5.4 Strategies for Recruitment and Retention

All three participating sites have active aphasia research programs and large recruitment pools for aphasic participants. We will utilize our established participant pool that has agreed to future contact for participation in studies to recruit for this study. These individuals will be contacted by telephone, email, or mail depending on their communication preference. The use of telehealth will likely facilitate strong participant retention rates due to the convenience of in-home therapy.

#### 5.4.1 Advertising

Recruitment will also be performed through local advertisement. We will adopt a strategy that is similar to what was used previously in our large treatment studies where advertisement to rehabilitation centers and clinics has yielded sufficient recruitment. An approved study flyer will be distributed to local clinics, hospitals and rehabilitation centers. Furthermore, we will also advertise to participants who have enrolled in previous aphasia clinical trials at all three sites. If our yield is low, we will update our recruitment plan to use local and state newspaper advertisements as needed. We also plan to advertise studies through statewide directories and site-specific lab websites in addition to university and/or site-specific lab social media accounts, per the IRB of records policies.

#### 5.4.2 Contacting Participants

During the recruitment and initial scheduling period, participants and/or their caregiver/family (as applicable), may be contacted via telephone, email correspondence, or traditional mailing service (whichever is preferred by the participant). Upon establishing

preferred communication preferences, follow-up appointments, changes in schedule, or other pertinent study related information will be relayed in the same manner, as expressed by the participant.

# 6.0 Study Intervention

# 6.1 Study Intervention Administration

The administration of SET is relatively simple: Subjects practice imitating in real-time 1minute scripts that consist of prerecorded videos (A/V speech model). Each video is presented through the SET treatment app made in house that is preloaded on the computer in the teletherapy kit. We will ask the participant or assistant to place the computer (with a highspeed video card) at a comfortable distance in front of the subject, showing a speaker whose face is visible below the nose. Subjects are fitted with headphones to minimize distractions and to better focus on the auditory speech. The A/V speech model involves a relatively slow speech rate and a high-speed video frame rate and the subject is asked to mimic the speech as closely as possible. Subjects usually mimic the speech almost in real-time while seeing and hearing the A/V model. A trained research staff member is present during each session to provide guidance according to pre-established guidelines and to ensure treatment compliance. At the beginning of the first 2-3 treatment sessions, the research staff member models the manner in which the participant should imitate the A/V speech model. The subject instructions are as follows: "Your goal is to speak along with the video and try to match the timing of your speech as closely as possible to the video. If you miss words or fall behind, try to catch up with the video and continue speaking."

Once subjects understand the approach (as per the judgment of research staff trained by an SLP), the SET session is started. When treatment begins, the participant observes/listens as the videorecorded script is presented in its entirety without mimicking. On successive presentations, the participant mimics the script in real-time. Once a given script (video) has been mimicked three times, a new script is presented and then practiced three times, and so on. Practicing each script three times is based on our experience suggesting that subjects improve considerably from the first to the third practice of a given script. A total of 39 scripts addressing various topics will be constructed. During the treatment session, a new script video is selected at random. In-house computer software is used to accomplish stimulus presentation, start and stop the treatment session, and keep track of treatment data (e.g., the average number of scripts trained per session and how many times a given script was trained during the course of treatment).

#### 6.1.1 No SET condition

During the no SET condition, the participant will not receive any specific form of therapy from the study. The purpose of the no SET condition is to assess whether SET provides a therapeutic benefit over the participants' current standard of care.

#### 6.1.2 Treatment and assessment setting

Once consent has been obtained and the local research team has established a study schedule for the participant, we will begin baseline testing and subsequent treatment. All baseline cognitive-linguistic testing will be performed via telehealth, and treatment will be

performed through the SET treatment app. We will request that a family member or friend be present during assessment and treatment sessions to assist with technology as needed. Headphones will be used to ensure high quality auditory stimuli. Breaks will be given as needed for those participants in testing or treatment as to not cause fatigue or stress in a new environment.

The optional MRI (at either 3- or 6-months post-intervention) will be performed at the local site's imaging center. Each participant will be provided ample time and orientation from the staff in order to feel comfortable with the scanner and time spent in the scanner.

#### 6.1.3 Dosing and Administration

Treatment dose is dependent on particular group randomization (3 weeks, 4.5 weeks, 6 weeks, no SET).

# 6.2 Measures to Minimize Bias: Randomization and Blinding Instructions

#### 6.2.1 Randomization

Once the participant is consented and enrolled in the study, his/her information is entered in the online clinical trial management system – Web Data Coordination Unit (WebDCUTM). Once the baseline data have been entered in WebDCU, the participant will be randomized to one of 3 SET groups (differing dose) or the control group (Figure 1).

A "Real-Time" randomization procedure will be implemented via the trial website on the WebDCUTM system (located at MUSC). Using the WebDCUTM, the local site's study staff will enter baseline and eligibility information for each subject prior to enrollment. If a subject's eligibility status is confirmed, WebDCUTM will make the treatment assignment based on the current status of treatment group distribution at each site, age group ( $\leq$ 70, >70 years), and aphasia severity (mild/moderate: AQ > 50, severe/very severe: AQ  $\leq$  50), as well as the overall balance of treatment assignments. Once a subject is randomized, the SLP or trained research staff will be made aware of the randomization assignment. The SLP or research staff will videorecord all behavioral assessments, and the recordings will be uploaded to Box at the conclusion of the treatment for centralized scoring.

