# **Screening & Randomization**

[figure not shown]
Informed consent, review eligibility, WAB-R^24, Apraxia of Speech Rating Scale 3.0 (ASRS 3.0), review of clinical images.

\*Assessments taken during screening will also be utilized as baseline data

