Videorecordings of assessments will be saved to the researcher's local password protected and encrypted computer. Videos will be immediatley uploaded to a HIPAA-compliant Box account. Once vidoes are confirmed to have been successfully uploaded to the Box account, research staff will immediately delete the video stored on the computer's harddrive. Participants will be asked to have a friend or family member (assistant) present to help with technology.

Once all assessments are complete, and the participant is found to have non-fluent aphasia as well as meets all eligibility criteria (section 5.1 and 5.2), the participant will be randomly assigned to one of four arms (Figure 1):

[figure not shown]

Figure 1. Overall study design. This diagram depicts the 3 different doses of SET (treatment arms) and the control arm. For clarity of visualization, the behavioral assessments are not depicted in this diagram, but are explained in Table 1 (Study Schedule) below. In brief, all participants will receive behavioral assessments one week before the initiation of therapy, then 1 week, 3 months, and 6 months after the conclusion of SET or no SET.

After randomization, a telehealth technology kit will be sent to the participant's home. Each kit will include:

- 1. A computer pre-loaded with the treatment applications, internet capeabilities for the telehealth platform, and Team Viewer, which will allow the SLP to see the participant's computer to help with initial set-up and troubleshooting.
- 2. A high-quality headset and microphone to maximize communication with research staff online.
- 3. A mouse for optional use.
- 4. A mobile WiFi hotspot if a participant does not have an adequate WiFi connection at home.

Participants will be asked to review and sign the SpARc Telehealth Technology Contract upon receipt of equipment. The Technology Contract will also be created in RedCap so the patient can sign virtually.

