#### 1.3.2 Baseline Assessments (Visit 1)

The baseline assessment visit will consist of the tests outlined below. All assessments are adapted to be administered online. A brief training session will take place before the administration of assessments to make sure that the participant and his/her assistant can demonstrate how to use controls in the telehealth platform to point to pictures on a shared screen. The assistant will also be instructed on how to alter the webcam to allow the clinician to view the participant completing different tasks.

Baseline testing (demographic and baseline characteristics can be seen in Table 3 and the remaining assessments in Table 1) will be done in all groups. Per the discretion of the SLP, baseline assessments can be completed over the course of 2-5 days, depending on the participant's ability and stamina. Descriptions of baseline assessments can be found in section 1.4, Study Assessments. Instructions for administering assessments can be found in specific assessment manuals. The order of baseline assessment administration after screening is as follows:

- 1. Verbs per Minute (VPM) discourse assessments
- 2. Modified Philadelphia Naming Test (PNT)
- 3. Stroke and Aphasia Quality of Life (SAQOL-39g)
- 4. Modified Charlson Comorbidity Index
- 5. Communicative Effectiveness Index (CETI)
- 6. Lexical Orthography Familiarity Test (LOFT)
- 7. Modified Epworth Sleepiness Scale (ESS)
- 8. Pyramids and Palm Trees Test (PPTT)
- 9. Matrix Reasoning Wechsler Adult Intelligence Scale III (WAIS-III)
- 10. Vertical Numerical Rating Scale-Face Rating Scale for post-stroke fatigue (NRS-FRS)
- 11. Modified Philadelphia Repetition Test (PRT)
- 12. Community Stroke Aphasic Depression Questionnaire (SADQ-10)

We will keep the order of test administration constant but will leave it to the clinical judgment of the SLP to determine appointment duration and number of days required for each individual participant to complete testing. Factors that the clinician will consider include severity of aphasia, overall endurance, and tolerance of testing. From experience with prior aphasia trials, these factors can vary between participants.

Schedule for screening, baseline assessments, intervention, and outcome measures can be seen below in Table 1:

	*D-f+- T		hedule of Activ		d	

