Assessment	Screening &	Baseline	nent recording ar Intervention	Follow-Up	Follow-Up	Follow-Up
	Randomization Visit 0 Days -5 to 0	Assessments Visit 1 Days 1-5 (+/-4 days)	Period Visits 2-30 a For 3, 4.5, or 6 weeks (+/- 3 days)	Visit 1 1-week post intervention b (+/- 3 days) c	Visit 2 3-month post intervention b (+/- 1 week) c	Visit 3 6-month post intervention b (+/- 1 week) c
Informed consent	Χ					
Review of eligibility criteria and randomization	Х					
Concomitant Aphasia Treatment				X		Х
Assess New Adverse Events			X	Χ		
Verbs per Minute (VPM)		Χ		Χ	X	X
Gathering of individual demographic and baseline characteristics (Table 3)		X				
NIH Stroke Scale (NIHSS)	X					
Western Aphasia Battery- Revised (WAB-R)	X d, e			Х	Х	Х
Quality of life assessment - Stroke and Aphasia Quality of Life (SAQOL-39g)		Х		X	X	X
Charlson Comorbidity Index		Χ				
Communicative Effectiveness Index (CETI)		X		X	X	
Lexical Orthography Familiarity Test (LOFT)		Х				
Modified Epworth Sleepiness Scale (ESS)						
Apraxia of Speech Rating Scale 3.0 (ASRS 3.0)	X d			X	Х	
Pyramids and Palm Trees Test (PPTT)		Х				
Matrix Reasoning - Wechsler Adult Intelligence Scale, Third Edition (WAIS-III)		Х				
Vertical Numerical Rating Scale-Face Rating Scale for post-stroke fatigue (NRS- FRS)		Х				
Modified Philadelphia Repetition Test (PRT)		X		X	Х	
Modified Philadelphia Naming Test (PNT)		X		X	Х	
Stroke Aphasic Depression Questionnaire (SADQ-10)		X				
MRI					(opt	ional)

Footnote: aNumber of visits depend on randomized arm. bFollow-up assessments can be completed over 1-5 days. cDefinitions for the follow-up visit target date and window provided in Table 2. dRepeat WAB-R/ASRS 3.0 measures prior to intervention if initiation of intervention period occurs >15 days post randomization. eUse of WAB-R scores obtained for other purposes, administered within 120-days before randomization, is allowed.

Note: In the event of technological difficulties, readministration of baseline or follow-up testing will be conducted within study timeline constraints to maintain the integrity of data collection.

Table 2. Follow-Up Visit Target and Visit Windows in Days						
Randomization	Follow-Up	Follow-Up	Follow Up			
Assignment	Visit 1	Visit 2	Visit 3			

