SET (any dose)	7 days after the last completed SET session +/-3 days	90 days after the last completed SET session +/-7 days	180 days after the last completed SET session +/- 7 days			
No SET a	54 days post-	137 days post-	227 days post-			
	randomization +/-7 days	randomization +/-11 days	randomization +/-11 days			

Footnote: aThe No SET target date for follow-up visits accounts for time to complete baseline assessments (5 days), and the window for the follow-up visits is widened to account for the window for baseline assessment visits (additional +/-4 days).

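### Baseline SAQOL-39g and, to a lesser degree, baseline VPM are scheduled after randomisation, and nothing withholds the arm until they are taken

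*Protocol*

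**What the plan says.** Protocol 1.3.1 closes Visit 0 with randomisation: once screening is complete and eligibility is met, "the participant will be randomly assigned to one of four arms". The schema in 1.2 marks this as Day 0. Section 1.3.1 goes on: "After randomization, a telehealth technology kit will be sent" to the home.

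Section 1.3.2 makes baseline testing a separate Visit 1 for every arm. VPM is item 1 and SAQOL-39g item 3 of a fixed 12-item order that follows screening. Table 1 puts Visit 1 at Days 1-5 with a window of 4 days either way. Footnote a of Table 2 counts 5 days of baseline testing after randomisation when it sets the No SET follow-up dates.

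On who knows the arm, 6.2.1 states "Once a subject is randomized, the SLP or trained research staff will be made aware of the randomization assignment". Section 4.1.1 says that neither research staff nor participants are blinded, and that the research staff both assess and treat.

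Two places point to an earlier baseline. Section 6.2.1 also says "Once the baseline data have been entered in WebDCU, the participant will be randomized", and the ASRS 3.0 entry in 1.4 has that instrument, a Visit 0 measure in Table 1, rated partly on the discourse samples used for baseline VPM. The schema adds "Assessments taken during screening will also be utilized as baseline data".

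**The concern.** When treatment cannot be blinded, the baseline is still one measurement that can be taken before anyone reacts to the allocation. The plan as scheduled gives that up. A participant told to expect six weeks without therapy may rate quality of life differently, or try less hard, than one about to start SET. Staff who know the arm may prompt or encourage differently.

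The baseline enters the analysis twice: SAP 7 subtracts baseline VPM to form the outcome and also uses it as a covariate, and SAP 11 does the same with the SAQOL-39g baseline. A baseline difference caused by knowing the arm would therefore pass into each SET-control estimate, the exploratory pooled test, and the effect-size criterion of 0.36 in protocol 9.2.2 and SAP 4. The planned baseline table would be unlikely to reveal it.

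**Working it through.** **1. Does baseline follow randomisation?** Table 2 answers this by arithmetic. Inputs: 5 baseline days and a 4-day widening of the windows (footnote a); a control period of 6 weeks, or 42 days; SET-arm offsets of 7, 90 and 180 days with windows of 3, 7 and 7 days.

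| | Visit 1 | Visit 2 | Visit 3 |
|---|---|---|---|
| Table 2, No SET, days after randomisation | 54 ± 7 | 137 ± 11 | 227 ± 11 |
| Baseline after randomisation | 5+42+7 = 54; 3+4 = 7 | 5+42+90 = 137; 7+4 = 11 | 5+42+180 = 227; 7+4 = 11 |
| Baseline before randomisation | 42+7 = 49; 3 | 42+90 = 132; 7 | 42+180 = 222; 7 |

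Only the second row reproduces the plan's figures.

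**2. What can *baseline data* in 6.2.1 mean?** The assignment needs only site, age group and AQ, all known at screening, and the schema counts screening assessments as baseline data. VPM is scored off-line from transcripts (1.4). Section 6.2.1 sends recordings for central scoring at the end of treatment, although 1.3.1 speaks of immediate upload. The likely meaning is the Visit 0 data, but the text does not say so.

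**3. What is protected?**

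| | SAQOL-39g | VPM |
|---|---|---|
| Source of the value | Participant's own ratings (1.4) | Recorded discourse |
| Scoring | Local site, no video (Table 4) | Central, blinded to arm and time point (6.2.2) |
| Control of administration | Manual and training | Also randomised topics, a time limit on procedural items, text-free books (8.1.2), and fidelity review of recordings (6.3.1, 6.3.3) |
| Left exposed | The rating itself | Participant effort, residual elicitation effects |

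**4. How large could a VPM effect be?** The documents give no size, so this is an illustration. Let d be the SET-minus-control shift in baseline VPM caused by knowing the arm, p the share of it still present at 3 months, and b the slope of 3-month VPM on baseline. The adjusted difference equals the 3-month difference minus b times the baseline difference, so

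bias = p·d − b·d = (p − b)·d.

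The pilot figures in 4.3.1 (SDs 3.9 and 4.8, SD of change 1.98, n=15) give

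- r = (3.9² + 4.8² − 1.98²)/(2 × 3.9 × 4.8) = 0.917
- b = 0.917 × 4.8/3.9 = 1.13

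The model also adjusts for WAB-AQ, site and age, so a lower slope is possible. Assuming r = 0.5, b = 0.5 × 4.8/3.9 = 0.62.

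| p | Bias, b = 0.62 | Bias, b = 1.13 | At d = 0.25 VPM |
|---|---|---|---|
| 0 | −0.62d | −1.13d | −0.15 to −0.28 |
| 0.5 | −0.12d | −0.63d | −0.03 to −0.16 |
| 1 | +0.38d | −0.13d | +0.10 to −0.03 |

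Signs reverse for d = −0.25. At the planning SD of 2, the p = 0 row is 0.08 to 0.14 SD. With p = 0, taking a true effect of 0.50 down to 0.36 (0.14 × 2 = 0.28 VPM) needs d of 0.28/1.13 = 0.25 to 0.28/0.62 = 0.45. Lifting a null effect to 0.36 (0.72 VPM) needs d of −0.64 to −1.17. No SD is given for SAQOL-39g, so no figure can be offered for it.

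**5. Would the baseline table show it?** For 60 versus 20 participants, SE = 3.9 × √(1/60 + 1/20) = 1.01 VPM, so the 95% half-width is about 2.0 VPM. A shift of 0.25 would not be visible.

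**The case against.** **The order is not settled for VPM.** Section 6.2.1 puts entry of baseline data before randomisation, and the ASRS 3.0 entry could mean that the discourse sample is recorded at Visit 0. If so, VPM is not exposed, though SAQOL-39g still is. The lower side of the Visit 1 window (1 − 4 = Day −3) would also allow testing before Day 0. These points stand as conflicts to reconcile. They do not displace Tables 1 and 2, and no text requires testing before Day 0. Nor does the ASRS wording force a Visit 0 sample: eligibility uses only that scale's spontaneous speech tasks (5.2), and its scoring is done later from recordings.

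**VPM is well defended.** Blinded scoring and monitored, standardised elicitation narrow the staff route considerably. This stands. A reader might infer that VPM scoring itself is compromised; section 6.2.2 rules that out. A reader might also infer that participants know their arm at baseline. The documents do not say when they are told, only that nothing delays it.

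**Withholding may not reduce net bias.** With an unexposed baseline the bias would be p·d, which is smaller in size than (p − b)·d only when p < b/2, that is below 31% (b = 0.62) to 56% (b = 1.13). The arithmetic is right. But a reaction still present at 3 months is the separate problem of an open-label follow-up, and a contaminated baseline is not a sound way to cancel it.

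**Little rides on it.** No formal test of SET against control is planned (9.1), and the 0.36 criterion appears in the sample-size sections but not in the selection rule (9.4.4, SAP 9). This limits the consequence. The estimates against control are still what the trial will report.

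**Conclusion.** The concern holds in limited form. The schedule places baseline VPM and SAQOL-39g after randomisation, the assessing staff are told the arm at that point, and no provision withholds it from them or from participants until the two measures are taken. Exposure is clear for SAQOL-39g. For VPM it is confined to participant effort and residual elicitation effects, and it depends on Table 1 rather than the ASRS wording being followed.

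Size and direction are unknown. The figure of 0.15 to 0.28 VPM rests on an assumed shift of 0.25, no persistence to 3 months, and slopes of 0.62 to 1.13; with full persistence the effect largely cancels at the pilot slope.

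A reader might infer that the choice of dose is unsafe. The documents do not support that. A shift shared by the three SET arms adds the same amount to each difference from control, so with a common SD the ranking is unchanged. Only a reaction that differed between durations could alter it, and nothing in the documents indicates one.

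**What to change.** - Keep randomisation and kit shipment at Day 0. Section 1.3.1 lists one kit for everyone, with a hotspot by need, so shipment need not reveal the arm. The Table 2 dates stay as they are.
- State in 1.3.1 and 6.2.1 that the assignment is not released to site assessors or participants until Visit 1 VPM is recorded and SAQOL-39g is completed. Central VPM scoring need not be finished.
- State in 6.2.1 that *baseline data* means the Visit 0 screening and stratification data.
- Reconcile the ASRS 3.0 entry in 1.4 with Table 1 on when the shared discourse sample is recorded. Reconcile 6.1.2, which sets the participant's study schedule before baseline testing, so that an arm-specific schedule is set only after release.
- For participants already randomised, report as a limitation that baseline testing followed disclosure of the arm.

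Cost: a small WebDCU change (release on a Visit 1 completion entry), text edits, and about a week's delay in scheduling SET sessions. Release falls at Day 5 + 4 = Day 9 at the latest, which leaves 15 − 9 = 6 days before the repeat-testing trigger in Table 1. It may come sooner, because the two measures are early in the fixed order. The change does not remove reactions at the unblinded follow-up visits.
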